4.5.4 Modified Rankin Scale

A pre-stroke mRS will be estimated at baseline.

At discharge/Day 5, 30 and 90 days after randomization, patients will be evaluated using mRS preferably in the clinic. If an in-person visit is not feasible, the patient can be evaluated by telephone ([Appendix 2](#)).

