6.4.1 Primary Efficacy Endpoint

The primary endpoint is the ordinal mRS score at Day 90. The distribution of the mRS scores will be compared between the treatment groups by a proportional odds model controlling for the randomization strata *and baseline mechanical thrombectomy planned status*. If the proportional-odds assumptions are not met, alternative assumption-free ordinal analysis on the mRS score will be used (Agresti 1980; Howard et al. 2012; Churilov et al. 2014). Further details about the assumption-free method will be described in the SAP. Superiority of tenecteplase over placebo will be declared if the p-value of the estimated treatment effect from the proportional odds model is ≤ 0.049 (two-sided). An unadjusted analysis will also be performed using the Wilcoxon-Mann-Whitney test.

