2.3 DETERMINATION OF SAMPLE SIZE

Approximately 456 patients will be enrolled in this study. Assuming the distribution of mRS scores at Day 90 in the two treatment arms as shown in [Table 1](#) and a 5% dropout rate in the study, approximately 228 patients in each treatment group will provide at least 90% power to detect the specified difference in the distribution of the mRS scores at the 2-sided 0.049 significance level (after adjustment for one efficacy interim analysis). This corresponds to being able to detect a common odds ratio (OR) of at least 1.76 (tenecteplase vs. placebo), with a total sample size of approximately 432 evaluable patients, assuming a 5% dropout rate.

Table 1 Assumed Distribution of 90-Day mRS in Use in Sample Size Determination

mRS	0	1	2	3	4	5	6
Tenecteplase (% of patients)	17	20	16	15	13	7	12
Placebo (% of patients)	13	13	12	14	18	12	18

mRS = modified Rankin Scale

The sample size estimation is highly dependent on the distribution assumption of 90-day ordinal mRS score for both treatment arms; thus, additional power calculation were performed with 456 total patients, assuming 5% drop-out rate, for different distribution scenarios on the mRS at Day 90, derived from previous stroke studies. These resulted in >88% and >99% power to detect the specified difference in the distribution of the mRS scores. For more details, see Section 6.1 of the Protocol.

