4.6 EFFICACY ANALYSIS

Efficacy analyses will be performed using the ITT population with patients grouped according to treatment assigned at randomization. Available data regardless of adherence to the protocol will be included in the efficacy analyses; this includes data from patients who discontinued prematurely from the study.

Deviation from the AHA/ASA treatment guidelines for standard of care (i.e. mechanical thrombectomy [MT] is planned for the patient but not performed due to various reasons) is considered an intercurrent event in this study. COVID-19 infections are considered another type of intercurrent event. COVID-19 infections during the follow-up period will be captured as AEs. In efficacy analyses, treatment policy strategy will be applied to both COVID-19 and non-COVID-19 intercurrent events. That is, all collected data will be used regardless of the occurrence of these intercurrent events.

Visit windows will be derived according to [Table 2](#) and applied for all clinical efficacy assessments. If there are multiple assessments within the same window, the one closest to the target time point will be used. Assessments that are outside of the defined windows will not be used in analysis, except they may provide a value for the last observation carried forward (LOCF) imputation in the case of mRS (see Section [4.9.1.1](#)).

Table 2 Definition of Visit Windows

Visit	Target Time	Window: mRS, GOS, BI, Neuro-QoL*	Window: NIHSS	Window: imaging
24 hours	24 hours	N/A	18 to 30 hours	18 to 30 hours
72-96 hours	84 hours	N/A	60 to 96 hours	60 to 120 hours
Day 5	5 days	4 to 6 days	5 to 6 days	N/A
Day 30	30 days	15 to 60 days	15 to 60 days	N/A
Day 90	90 days	61 to 120 days	61 to 120 days	N/A

BI = Barthel Index; GOS = Glasgow Outcome Scale; mRS = modified Rankin Scale; Neuro-QoL = Quality of Life in Neurological Disorders; NIHSS = National Institutes of Health Stroke Scale.

* Assessed only at Day 90 Visit

All analyses of efficacy endpoints (primary, secondary, and exploratory) will be evaluated for superiority. Analyses will be adjusted for all or a subset of the following variables:

- Age (≤ 70 vs. > 70 years of age)
- Type of occlusion (ICA/M1 vs. M2)
- Baseline NIHSS (≤ 15 vs. > 15)
- Randomization site (ECC vs. nECC)
- Mechanical thrombectomy planned (Yes vs. No)
- Protocol version (Protocol V1-4 vs Protocol V5).

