4.6.5 Subgroup Analyses

In addition to the exploratory subgroup analyses specified in Section 4.6.3.1, the primary efficacy endpoint will also be analyzed on the following subgroups:

- Age: <80 vs ≥ 80 years
- Baseline NIHSS: ≤ 15 vs > 15
- Baseline infarct volume: <20 mL, ≥ 20 mL and <50 mL, ≥ 50 mL
- Time (in hours) between stroke onset to randomization: <16 hours vs ≥ 16 hours
- Baseline occlusion type: ICA vs M1 vs M2
- Protocol version: Protocol V1-4 vs Protocol V5
- Mechanical thrombectomy planned at baseline: Yes vs No
- Mechanical thrombectomy performed (defined as successful clot manipulation): Yes vs No

- Time (in minutes) between study drug administration and groin puncture: groups defined by tertiles of the time variable. The analysis will include all patients who had groin puncture performed regardless of final performance of mechanical thrombectomy.

These subgroup analyses will be conducted using the same imputations and analysis methodology as the primary efficacy analysis (see Section 4.6.1), but proportionality of odds will not be re-evaluated for each subgroup.

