4.9.1.2 Multiple Imputation

Missing mRS data will be imputed using a sequential regression method. Particularly, mRS will be sampled from a multinomial distribution. This distribution will be estimated by ordinal logistic regressions, using baseline covariates and the previous mRS value.

The ordinal logistic regressions estimate the cumulative odds for achieving an mRS outcome of at most k :

$$\text{logit}[\Pr(mRS_t \leq k)] = \alpha_{kt} + X\beta_t + mRS_{t-1}\delta_t$$

where t is the time point index (Day 5, Day 30, Day 90), $k = 0$ to 5 , α_{kt} are intercepts, X is the design matrix for the baseline covariates and β_t are the corresponding regression coefficient vectors, and mRS_{t-1} is the previous mRS result (baseline, Day 5 or hospital discharge, or Day 30) with its coefficient δ_t . The list of covariates will include age, sex, race (white vs. non-white), baseline NIHSS, occlusion type and discharge destination (home vs. non-home).

Separate regressions will be fitted for each treatment group to avoid any assumptions about the treatment effect. In order to limit the number of parameters and prevent estimation issues, it will be assumed that the covariate effects β_t and δ_t do not depend on k (the proportional odds assumption). The model may be revised if estimation issues are encountered (e.g. quasi-complete separation). Logit is the usual link transformation, associated with a logistic regression.

For each fixed value of Δ , imputation is carried out in the following steps. These steps are repeated to impute missing mRS first at Day 30, then at Day 90 (using imputed Day 30 results):

- Fit the ordinal logistic regressions for mRS at time t , separately in the TNK and placebo groups.
- For patients with missing mRS at time point t , obtain the predicted cumulative probabilities. In the placebo group, use the probabilities predicted by the model. In the TNK group, recalculate the probabilities using the following equation.

$$\text{logit}[\Pr(mRS_t \leq k)] = \widehat{\alpha}_{kt} + X\widehat{\beta}_t + mRS_{t-1}\widehat{\delta}_t - \Delta$$

where $\widehat{\alpha}_{kt}$, $\widehat{\beta}_t$ and $\widehat{\delta}_t$ are the estimated coefficients from the TNK model. The penalty term Δ reduces the odds for a favorable outcome. This penalty will only be applied the first time mRS is missing for the patient; its effect will be propagated to subsequent time points by the mRS_{t-1} term in the regression.

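### The primary model leaves out three baseline variables that are collected and plausibly prognostic; prespecifying them is a cheap way to gain a little power

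*SAP*

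**What the plan says.** SAP 4.6 sets the covariates for the efficacy models with "Analyses will be adjusted for all or a subset of the following variables". The list is age group, occlusion type, NIHSS group, site type, planned thrombectomy and protocol version, each with two levels. Appendix 5 may then remove some of them to avoid small cells. Protocol 6.4.1 compares the Day 90 mRS distributions "by a proportional odds model controlling for the randomization strata" and adds planned-thrombectomy status.

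Three other baseline variables are in neither list, yet the documents show that they are available:

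- **Pre-stroke mRS.** Protocol 4.5.4: "A pre-stroke mRS will be estimated at baseline". Eligibility limits it to 0, 1 or 2. SAP 4.3 defines and summarizes a baseline mRS.
- **Ischemic core volume.** It decides eligibility (under 70 mL in the main imaging criterion). SAP 4.6.5 uses baseline infarct volume as a subgroup variable, and SAP 4.6 uses the local baseline reading to compute infarct growth.
- **Onset-to-randomization time.** SAP 4.6.5 lists it among the subgroups: "Time (in hours) between stroke onset to randomization".

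The power statement in SAP 2.3 is that "approximately 228 patients in each treatment group will provide at least 90% power", "at the 2-sided 0.049 significance level (after adjustment for one efficacy interim analysis"). The protocol synopsis attributes this power to the Wilcoxon-Mann-Whitney test, which uses no covariates.

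**The concern.** In an ordinal outcome model, prespecified prognostic covariates raise power and account for chance imbalance. Randomization is not stratified on any of these three. The documents also hint that the authors consider some of them informative. The imputation model in SAP 4.9.1.2 has a term that "is the previous mRS result (baseline, Day 5 or hospital discharge, or Day 30"), and Protocol 1.3 refers to a strong relation between time to reperfusion and disability, an interval that includes onset-to-randomization time.

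The planned adjustment is also thin. Crossing five two-level variables with treatment gives 2^6 = 64 cells, or 456/64 = 7.1 patients on average. Appendix 5 discards any combination whose smallest cell is at or below 1% of the ITT set (4.56 patients if 456 are enrolled), so one or more planned covariates may well be dropped.

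At stake is some power in the primary test and in functional independence, which is first in the secondary hierarchy and uses the same covariates.

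**Working it through.** **Inputs.** From SAP 2.3: 456 enrolled, 432 evaluable (216 per arm), two-sided alpha 0.049 (critical value 1.969), common OR 1.76, and the assumed Day 90 mRS distributions in Table 1. The documents give no prognostic strength for any covariate, so strengths below are assumptions.

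**Step 1: reproduce the stated power without covariates.**

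- Mean category proportions over the two arms: 0.150, 0.165, 0.140, 0.145, 0.155, 0.095, 0.150. One minus the sum of their cubes is 0.9784.
- Probability that a tenecteplase patient does better than a placebo patient, counting ties as half: 0.58955.
- Null SE = sqrt[(0.9784/12) × (2/216)] = 0.02748. Power = Φ(0.08955/0.02748 − 1.969) = 90.2%. With the variance under the alternative it is 90.5%.
- Cross-check with the Whitehead formula, Φ(log OR × sqrt(432 × 0.9784/12) − 1.969): 90.9% at the common OR fitted to Table 1 (1.74) and 91.7% at the stated 1.76.

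The plan's figure stands and takes no credit for any covariate.

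**Step 2: effect of omitting a prognostic score.** Let U be a standard normal score standing for the three variables combined, with log-OR g per SD beyond the planned covariates. Let the planned covariates have combined log-OR h per SD. The placebo distribution is held at Table 1 and the marginal OR at 1.76. Power is Φ(log OR/SE − 1.969), using the expected information of the proportional-odds model at N = 432.

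| g | h = 0: without U → with U | Gain (points) | h = 0.7: without U → with U | Gain (points) |
|---|---|---|---|---|
| 0.2 | 91.2 → 91.6% | 0.4 | 94.9 → 95.2% | 0.3 |
| 0.4 | 91.2 → 92.6% | 1.5 | 94.8 → 95.8% | 1.0 |
| 0.5 | 91.2 → 93.3% | 2.2 | 94.7 → 96.2% | 1.5 |
| 0.7 | 91.2 → 94.9% | 3.7 | 94.4 → 97.0% | 2.6 |
| 1.0 | 91.2 → 97.1% | 5.9 | 94.0 → 98.3% | 4.2 |

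Gains are taken before rounding. If g = 0 the gain is zero.

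**Step 3: where the gain comes from.** At h = 0 and g = 0.5, adding U moves the OR from 1.76 to 1.81 and the SE of the log-OR from 0.1703 to 0.1709. So log(1.76)/0.1703 = 3.32 becomes log(1.81)/0.1709 = 3.47. The odds ratio moves away from 1 while the SE rises slightly. The loss from omission is therefore attenuation, not a wider interval on the log scale.

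**Step 4: a smaller true effect.** At marginal OR 1.5 with h = 0, power is 66.5% without U. With U it is 69.0% (g = 0.4), 70.3% (0.5), 73.6% (0.7) or 79.3% (1.0).

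**The case against.** The strongest reply is that nothing here is wrong. The model adjusts for all four stratification factors, planned thrombectomy and protocol version. Leaving out further covariates does not bias the test under the null, and no stated figure depends on them. All of that stands.

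The evidence for prognostic strength within the documents is also weak:

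- Pre-stroke mRS is an estimated status before the event, confined to 0–2; it does not measure disability from this stroke. Core volume and time are also narrowed by the entry limits.
- The imputation model serves only the tipping-point analysis, and it contains neither core volume nor onset time.
- Listing a variable as a subgroup concerns differences in effect. The same list includes thrombectomy performed, which is known only after randomization.

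These points limit the likely size. They do not give a reason for leaving out variables that cost nothing to collect.

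A reader might infer a larger loss by applying the linear-model variance factor 1 − ρ² with ρ = 0.5 to the 90%, giving about 96%, a gain of 6 points, or 432 × 0.25/0.75 = 144 patients. The documents do not support this. No correlation is given anywhere. The calculation also starts from the unadjusted power instead of the planned adjusted model. And it treats the loss as a larger variance, which is not how a proportional-odds model behaves. That strength corresponds roughly to the bottom row of the table (g = 1.0 is a latent correlation of about 0.48), the most favorable case considered.

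**Conclusion.** The omission is a modest loss of efficiency and the remedy is a cheap improvement. The three variables are collected, are plausibly prognostic and are left out without explanation.

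At the planning effect, the gain from adding them is about 0.3 to 1.5 power points for a combined log-OR of 0.2 to 0.4 per SD. For 0.5 to 1.0 on top of informative planned covariates it is about 1.5 to 4 points. It is larger if the planned covariates carry little information or the true OR is nearer 1.5. These figures rest on assumed values of g and h and on the Table 1 placebo distribution; the documents do not allow a single number.

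A reader might also conclude that the primary analysis is biased, imprecise or underpowered. It is none of these on the plan's own assumptions: type I error is intact, the log-OR standard error is not inflated, and the power of at least 90% reproduces.

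**What to change.** Before unblinding, and decided by blinded staff, prespecify three main effects in SAP 4.6 and 4.6.1 for the proportional-odds primary model and the functional-independence logistic model:

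- pre-stroke mRS (0, 1, 2);
- core volume, continuous, for example log(volume + 1), with DWI volume where perfusion imaging was inadequate;
- onset-to-randomization time, continuous.

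Enter them outside the Appendix 5 cell-size selection, which cannot handle continuous variables. There is a precedent: protocol version is already included by default ahead of that selection, and it already goes beyond the covariates named in the protocol. State a simple rule for missing baseline values, such as the pooled median with a missing indicator. Align Protocol 6.4.1. Leave the stratified GenOR fallback on the categorical strata. If the sponsor prefers the present list, one sentence of justification in the SAP would do.

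The cost is wording and about four parameters (two for pre-stroke mRS and one each for the others), plus any missing indicators. The reported odds ratio becomes conditional on more covariates, and there is no gain if the GenOR fallback is used. The proportional-odds check in SAP 4.6.1 tests the whole model. With seven mRS levels, four added parameters bring 4 × 5 = 20 more degrees of freedom, so the SAP should say whether that check is run with or without the added terms. No new data are needed.

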In order to avoid small number of patients in the resulting strata, some variables may be removed from this list and not be adjusted for. The algorithm to perform this assessment is provided in [Appendix 5](#).

For endpoints that are based on the imaging data where both local and central reader's evaluation are collected, the central reader's evaluation will be used for analysis. Post-baseline final infarct volume will only be recorded by the central reader. The local recording for the baseline image will be used to calculate change from baseline in final infarct growth at 72-96 hours (or discharge if patient is being discharged prior to 72-96 hours visit).

Analyses of NIHSS, BI and GOS will only utilize data collected in-person or by telemedicine. NeuroQoL will only utilize data collected in-person. If any of these assessments are conducted by a mode that is not allowed for the assessment, the data will be listed, but excluded from analysis and not replaced by imputations.

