4.6.1 Primary Efficacy Endpoint

The primary endpoint is the ordinal mRS score at Day 90. mRS is an assessment of disability with values from 0 (no symptoms at all) to 5 (severe disability); death will be scored as a 6. During the study, mRS is collected at Baseline, Day 5 or hospital discharge, and 30 and 90 days after randomization. If death occurs prior to a scheduled assessment day, the mRS will be considered available and will be set to 6. The methodology for imputations related to the primary endpoint is described in Section [4.9.1.1](#).

The distribution of mRS at Day 90 will be summarized descriptively, and plotted using Grotta bars.

Analysis of the primary endpoint will test the hypothesis as follows:

$$H_0: OR_{\{TNK \text{ vs Placebo}\}} = 1 \text{ vs. } H_1: OR_{\{TNK \text{ vs Placebo}\}} \neq 1,$$

where $OR_{\{TNK \text{ vs Placebo}\}}$ stands for the overall odds ratio of achieving a lower level vs. higher level mRS between the tenecteplase and the placebo arms. Superiority of tenecteplase over placebo will be declared if the p-value of the estimated treatment effect is ≤ 0.003 (two-sided) at the efficacy interim analysis or ≤ 0.049 (two-sided) at the final analysis, after adjustment for one efficacy interim analysis.

In case there are issues with fitting the proportional odds model (such as e.g. a quasi-complete separation), the stratified Wilcoxon-Mann-Whitney Generalized Odds Ratio statistic (WMW GenOR) as described below will be employed. Otherwise, the proportional odds assumption will be tested. For this purpose, a proportional odds model will be fitted for the Day 90 mRS outcome, which will include treatment and adjusting variables. If the p-value for the overall score test of the proportional odds hypothesis is > 0.05 , the proportional odds assumption will be deemed acceptable. The assessment of the proportional odds assumption will be independent of the results from the primary efficacy analysis from the proportional odds model.

If the proportional odds hypothesis is not rejected, the parametric proportional odds model described above will be used to analyze the primary efficacy endpoint. The estimated common odds ratio of a lower mRS score (better outcome) will be presented for treatment (TNK vs. placebo). The corresponding Wald p-value and 95% CI will also be obtained.

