If the proportional odds hypothesis is rejected, the stratified WMW GenOR will be computed to compare the odds of having a lower mRS in the treatment group compared to placebo. This method does not require the proportional odds model assumption and is easily interpretable, computationally simple, and allows for confidence intervals to be constructed (Churilov et al. 2014). See details in [Appendix 4](#).

An unadjusted analysis of mRS distributions by treatment group will also be performed using the Wilcoxon-Mann-Whitney test (PROC NPAR1WAY) as supportive analysis.

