4.6.2.1 Functional Independence

A patient with functional independence is defined as having an mRS of 0–2 at Day 90. The proportion of patients with functional independence will be analyzed using logistic regression. The model will be adjusted as specified in Section 4.6. Observed counts and percentages for tenecteplase and placebo arms, and model based odds ratio, corresponding Wald 95% CI and p-value will be produced. This analysis will be performed with the same imputations used in the primary analysis (see Section 4.9.1).

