- Draw mRS at time t from the above distribution, with these additional considerations:
 - (a) Intermittently missing mRS cannot be imputed with mRS=6. Where mRS=6 is generated for imputation, mRS=5 will be imputed instead.
 - (b) Once mRS=6 is imputed, it will be propagated to all subsequent missing time points.

Note that by this algorithm, all ITT patients with baseline covariates will have Day 90 either observed or imputed. The process will be repeated to obtain 100 independent copies of the imputed dataset.

To analyze the multiply imputed data, apply the primary analysis model to each of the imputed dataset to arrive at 100 estimated treatment effects, $\gamma^{(m)}$ and their standard errors $S^{(m)}$, $m = 1$ to 100. The multiple imputation estimate and its standard error are then provided by the multiple imputation inference (SAS PROC MIANALYZE). The confidence interval and p-value can also be obtained from these estimates.

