24. Extensive early ischemic change (hypodensity) on non-contrast CT estimated to be >1/3 MCA territory, or significant hypodensity outside the $T_{max}>6s$ perfusion lesion that invalidates mismatch criteria (if patient is enrolled based on CT perfusion criteria)
25. Significant mass effect
26. Acute symptomatic arterial occlusions in more than one vascular territory confirmed on CTA/MRA (e.g., bilateral MCA occlusions, or an MCA and a basilar artery occlusion)
27. Evidence of intracranial tumor (except small meningioma) acute intracranial hemorrhage, neoplasm, or arteriovenous malformation

End of Study

The end of this study is defined as the date when the last patient, last visit (LPLV) occurs or the date at which the last data point required for safety follow-up is received from the last patient, whichever occurs later. The end of the study is expected to occur 90 days (± 14 days) after randomization of the last patient in (LPI) the study.

Length of Study

The total length of the study, from screening of the first patient to LPLV, is expected to be approximately 3 years.

Investigational Medicinal Products

Test Product (Investigational Drug)

The investigational medicinal product (IMP) for this study is tenecteplase. The recommended total dose for this study is weight-based with 0.25 mg of tenecteplase per kg, not exceeding a maximum dose of 25 mg. A single bolus dose should be administered over 5 seconds based on patient weight.

Comparator

Placebo is being used as the comparator since a thrombolytic is only FDA-approved in the United States for use out to 3 hours, and the standard of care guidelines support use out to 4.5 hours.

Statistical Methods

Primary Analysis

The primary endpoint is the ordinal mRS score at Day 90. The distribution of the mRS scores will be compared between the treatment groups by a proportional odds model controlling for the randomization strata and baseline mechanical thrombectomy planned status. If the proportional-

Tenecteplase—Genentech, Inc.

38/ Statistical Analysis Plan ML40787

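### The SAP's cell-size rule makes the protocol's five-variable primary model practically unreachable, for a reason that does not apply to a main-effects proportional odds model

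*SAP*

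**What the plan says.** Protocol 6.4.1 compares the Day 90 mRS distributions "by a proportional odds model controlling for the randomization strata" and planned thrombectomy status. The synopsis reproduced in SAP Appendix 1 says the same: "controlling for the randomization strata and baseline mechanical thrombectomy planned status". The four strata are age, occlusion type, baseline NIHSS and randomization site, so the model has five covariates.

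SAP 4.6 loosens this. "Analyses will be adjusted for all or a subset of the following variables" introduces six items, the sixth being protocol version, and the section adds that "some variables may be removed from this list and not be adjusted for". The reason given is to avoid small numbers in the strata that result. Appendix 5 supplies the rule:

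- cross each candidate set with treatment;
- discard it if the smallest cell is 1% of the full ITT set or less;
- among the survivors, take the longest set, then the one with the largest smallest cell.

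Protocol version is added by default, outside this selection. The sample code in Appendix 3 lists only the four stratification factors, in both the primary and the tipping-point blocks.

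SAP 4.6.1 already has a separate route for fitting trouble. "In case there are issues with fitting the proportional odds model", the analysis moves to the stratified generalized odds ratio (WMW GenOR). The same happens when the score test fails: "If the proportional odds hypothesis is rejected, the stratified WMW GenOR will be computed".

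**The concern.** One confirmatory model has three covariate lists: five variables in the protocol, all or a subset of six in SAP 4.6, and four in the Appendix 3 code. If the cell rule is as strict as it looks, the protocol's list is almost never the one fitted, and factors that stratified the randomization may leave the primary analysis.

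A small-strata reason is sound for methods that form strata: the stratified WMW GenOR, van Elteren's test and the stratified log-rank test. The proportional odds model and the functional independence logistic model estimate one coefficient per binary covariate from marginal information and do not need every crossed cell filled. What is at stake is precision, and whether a reader of the protocol can tell which model will be run.

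**Working it through.** **The plan's own figure.** Inputs from SAP 2.3: 432 evaluable patients, two-sided 0.049 (z = 1.969), odds ratio 1.76 and the Table 1 distributions, for which 1 − Σp̄³ = 0.9784. Whitehead's formula gives power Φ(ln 1.76 × √(432 × 0.9784 / 12) − 1.969) = Φ(0.565 × 5.935 − 1.969) = Φ(1.386) = 91.7%. The Wilcoxon normal approximation on Table 1, with probability of a better outcome 0.58955, gives 90.5%. The stated figure of at least 90% is reproduced. It is unadjusted, so it does not depend on Appendix 5.

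**Cells.** L binary variables crossed with treatment give 2^(L+1) cells. Three variables give 16, as Appendix 5 states; five give 64. The threshold is 1% of 456 = 4.56, so each cell needs at least 5. The mean is 456/64 = 7.1, or 6.75 with 432 patients.

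**Consequences that need no assumed margins.** Keeping all five requires:

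- 64 × 5 = 320 of the 456 patients (70%) placed by the rule alone;
- at least 32 × 5 = 160 patients (35%) at each level of each variable;
- at least 16 × 5 = 80 patients (17.5%) in each pair of levels, including M2 with thrombectomy planned, although SAP section 2 expects M2 patients generally not to have endovascular therapy.

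Keeping just the four strata (32 cells) needs at least 16 × 5 = 80 patients at each level, so nECC enrolment below 17.5% rules that out.

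**Chance of keeping all five, every margin 50/50 (most favourable).**

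| Setting | Calculation | Chance |
|---|---|---|
| 456, independent cells | P(Poisson(7.125) ≥ 5)^64 = 0.8381^64 | 1.2 × 10⁻⁵ |
| 432, independent cells | P(Poisson(6.75) ≥ 5)^64 = 0.8030^64 | 7.9 × 10⁻⁷ |
| 456, blocked randomization | simulated | 7.9 × 10⁻⁵ |
| 432, blocked randomization | simulated | 2.8 × 10⁻⁶ |
| 16 equal strata, 14 per arm | P(5 ≤ Bin(14, 0.5) ≤ 9)^32 = 0.8204^32 | 0.18% |
| 456, perfect 1:1 in all 32 covariate cells | simulated | 2.2% |

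**Which variables survive.** The documents give no margins, so these are assumed. Appendix 5 was simulated with permuted blocks of 4 in 16 strata and 5% loss from 456.

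- Over nine unbalanced mixes (nECC 5–50%, M2 20–50%, NIHSS above 15 in 10–45%), all five were kept in 0 of 7,200 trials and all four strata in 0 of 7,200. On average 2.5 to 3.0 of the five were kept. NIHSS was dropped in 3–96% of trials, depending on the mix.
- In a second set of five mixes (M2 30–40%, nECC 10–40%), planned thrombectomy was dropped in 55–99% and site in about 100% when nECC was 20% or less. In three of these mixes NIHSS was essentially never dropped.
- At the favourable end, with the other strata 50/50, all four strata were kept in 98–99% at nECC 40–50%, 64% at 30%, 20% at 25% and 1% at 20%.

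**Cost in power.** N = 432, conditional odds ratio 1.76, assumed log-odds for NIHSS −0.6/−1.0/−1.4 (weak/middle/strong), age −0.5/−0.7/−0.9 and M2 +0.3:

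| Setting | Primary: six main effects vs Appendix 5 | Functional independence |
|---|---|---|
| Weak effects | 91.2 vs 91.1% | 81.1 vs 80.8% |
| Middle | 91.9 vs 91.5% | 79.4 vs 79.1% |
| M2 20%, strong effects | 90.9 vs 88.8% | 76.2 vs 74.4% |

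**Does the larger model fit?** With nECC at 5% or 12%, the six-covariate proportional odds model was fitted in all 12,000 simulated trials at N = 228 and N = 432. In the functional independence model one covariate coefficient diverged in 0–1 of 3,000 trials at N = 432 and in 1–32 of 3,000 at N = 228. The treatment estimate was finite throughout.

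**The case against.** The strongest reply is that little is lost. The rule is pre-specified and deterministic and uses no outcome values, so it gives the analyst no room to choose. Simulated type I error as written is 0.048 and 0.041 against 0.049. In two of the three power settings the primary model loses only 0.1 to 0.4 points. All of that stands and limits the weight of the point.

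Other objections stand in part:

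- Adding protocol version means that the protocol's exact five-variable list would still not be fitted. True, but all five protocol covariates would be in the model, and version is already the SAP's default.
- Appendix 5 does not say clearly whether version is crossed by default. The simulated figures take it as uncrossed. If it is crossed, five variables plus version need 128 × 5 = 640 patients, more than 456, and more stratification factors are lost.
- The margins and prognostic effects are assumed, so the share of trials that drop NIHSS shows only that the result depends on enrolment.
- The Appendix 3 list may be leftover sample code, since the SAP says that it was developed from protocol version 4. It still needs correcting.
- Protocol 6.4.2 adjusts the secondary logistic models only as appropriate, so a reduced set for functional independence does not contradict the protocol. The argument there is that the stated reason does not fit.
- One rule keeps the proportional odds model and its WMW GenOR fallback on the same variables, and the fix separates them. This is a real cost, though a small one.
- The documents do not show whether the efficacy interim had taken place when the SAP was approved. The change therefore has to be made while the team is still blinded.

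**Conclusion.** The concern holds. The 64-cell count and the 35% and 17.5% minimums come from the documents alone. They put the protocol's five-variable model out of practical reach: about 10⁻⁵ under even margins, and at most about 2% under idealised balance. The stated reason fits methods that form strata and does not fit the primary model or the functional independence model. Which factors are lost, and how often, rests on assumed margins. The power loss of about 0 to 2 points rests on assumed prognostic effects. Type I error and the planned 90% power are not in question. The SAP should be corrected, but the point does not threaten the trial's conclusion.

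**What to change.** For the primary ITT proportional odds model, at interim and final, and for the full-ITT functional independence model, pre-specify main effects for age, occlusion type, baseline NIHSS, randomization site, planned thrombectomy and protocol version. Do not apply Appendix 5 to these two. They belong together because SAP 4.6.2.1 says "This analysis will be performed with the same imputations used in the primary analysis".

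- Keep the 4.6.1 switch to WMW GenOR when the primary model cannot be fitted.
- Functional independence has no fallback. Use the Appendix 5 set if a coefficient is not estimable; that set converged in all 34 simulated trials with a diverging coefficient.
- Keep Appendix 5 for methods that form strata and for the other logistic, subgroup and small-subset models.
- Align both Appendix 3 blocks with the fixed list. The tipping-point analysis must follow, because SAP 4.9.1.2 says to "apply the primary analysis model to each of the imputed dataset".
- State that the WMW GenOR fallback adjusts for a smaller set.

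The cost is SAP wording and a small program change before unblinding, with no patients, data or alpha. When proportional odds holds, the score test still rejects in about 5% of trials with either covariate set, and the switch to WMW GenOR then also shrinks the adjustment set. With that two-step procedure, simulated type I error is 0.050 with the fix against 0.048 as written (base mix), and 0.046 against 0.041 (M2 20%, strong effects), Monte Carlo standard error 0.003. Two-step power is 91.1 vs 91.0%, 91.8 vs 91.2% and 90.6 vs 88.6%.
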